3.8. Visit Definitions

3.8.1. Definition of Key Dates and Study Day

Study Days are calculated from the first dosing date of study drug and derived as follows:

- For postdose study days: Assessment Date – First Dosing Date + 1
- For days prior to the first dose: Assessment Date – First Dosing Date

Therefore, study day 1 is the day of first dose of study drug administration.

Baseline Value is defined as the last value obtained on or prior to the first dose of study drug.

Last Dose Date is defined as the latest dose date of any study drug as recorded on the Study Drug Administration eCRF (i.e., VES, VRC07-523LS, CAP256V2LS).

Last Study Date is the latest clinic visit date, and/or the laboratory visit dates, and/or latest AE onset date and end date, whichever is latest, including the any follow-up visit dates for participants who completed study.

Last Exposure Date is defined as last study date for all participants who receive VRC07-523LS and/or CAP256V2LS infusion. This date is defined considering the prolonged exposure of VRC07-523LS and CAP256V2LS after the last dose date through the end of study.

ATI Start Date is defined as the last stop date of Non-Study Antiretroviral (ARV) Medication between the study drug start and discontinuation, plus one day.

ART Restart Date is defined as the start date of resuming ART or compatible regimen after ATI start on Non-Study ARV Medication eCRF form.

3.8.2. Analysis Visits

The nominal visit as recorded on the eCRF or lab date will be used when data are summarized by visit. Any data relating to unscheduled visits will not be assigned to a particular visit or time point and in general will not be included in by-visit summaries. However, the following exceptions will be made:

- An unscheduled visit prior to the first dose of study drug may be included in the calculation of baseline value, if applicable.
- Unscheduled visits after the first dose of study drug will be included in determining the maximum postbaseline toxicity grade and time to event analyses.
- For participants who prematurely discontinued from the study drug, early termination (ET) data will be summarized as a separate visit, labeled as “Early Study Drug Discontinuation”.
- Data obtained after the follow-up visit or last exposure date (whichever is later) will be excluded from the summaries but will be included in the listings.

3.8.3. Selection of Data in the Event of Multiple Records for a Visit

Depending on the statistical analysis method, single values may be required for each visit. For example, change from baseline by visit usually requires a single value, whereas a time-to-event analysis would not require 1 value per visit.

If multiple valid, non-missing, numeric measurements exist on the same nominal visit, records will be chosen based on the following rules if a single value is needed:

- In general, the baseline value will be the last non-missing value on or prior to the first dosing date of study drug, unless specified differently. If multiple measurements occur on the same day, the last non-missing value prior to the time of first dosing of study drug will be considered as the baseline value. If these multiple measurements occur at the same time or the time is not available, the average (geometric mean for HIV-1 RNA and arithmetic mean for others) of these measurements will be considered as the baseline value.

- For postbaseline visits, the value for the scheduled visit only will be used. If there is more than one record on the selected visit, the average will be taken (geometric mean for HIV-1 RNA and arithmetic mean for others), unless otherwise specified.

If multiple valid, non-missing, categorical measurements exist on the same nominal visit, records will be chosen based on the following rule if a single value is needed:

- For baseline, the last available record on or prior to the first dose of study drug will be selected. If there are multiple records with the same time or no time recorded on the same day, the value with the lowest severity will be selected (e.g., normal will be selected over abnormal for safety ECG findings).
- For postbaseline visits, the value for the scheduled visit only will be used. If multiple records are available for a scheduled visit, the most conservative value within that visit will be selected (e.g., abnormal will be selected over normal for safety ECGs).

4. SUBJECT DISPOSITION

4.1. Participant Enrollment and Disposition

Key study dates (i.e., first participant screened, first participant enrolled, last participant enrolled, last participant last visit for the primary endpoint, and last participant last visit for the clinical study report) will be provided.

A summary of participant enrollment will be provided by each investigator within a country. The summary will present the number and percentage of participants enrolled. The denominator for the percentage calculation will be the total number of participants analyzed.

A summary of participant disposition will be provided. This summary will present the number of participants screened, the number of participants who did not meet all eligibility criteria and not enrolled, the number of participants who met all eligibility criteria but were not enrolled with reasons participants not enrolled, the number of participants enrolled, and the number of participants in each of the categories listed below:

- Safety Analysis Set
- Completed study drug
- Did not complete study drug with reasons for premature discontinuation of study drug
- Completed study
- Did not complete the study with reasons for premature discontinuation of study

For the status of study drug and study completion and reasons for premature discontinuation, the number and percentage of participants in each category will be provided. The denominator for the percentage calculation will be the total number of participants in the Safety Analysis Set. In addition, a flowchart will be provided to depict the disposition.

The following by-participant listings will be provided by participant identification (ID) number in ascending order to support the above summary tables:

- Reasons for premature study drug or study discontinuation

4.2. Extent of Study Drug Exposure

A participant's extent of exposure to study drug will be generated from the study drug administration data. Exposure data will be summarized.

4.2.1. Duration of Exposure to Study Drug

Duration of exposure to study drug will be defined as the last exposure date minus the first dose date plus 1, regardless of any temporary interruptions in study drug administration, and will be expressed in weeks using up to 1 decimal place (e.g., 4.5 weeks).

Duration of exposure will be summarized using descriptive statistics (n, mean, SD, median, Q1, Q3, minimum, and maximum) and as the number (i.e., cumulative counts) and percentage of participants exposed through the following periods: 1 day, 2 weeks, 4 weeks, 6 weeks, 8 weeks, 10 weeks, 12 weeks, 14 weeks, 16 weeks, 18 weeks, 20 weeks, 34 weeks, 48 weeks, and 59 weeks.

Summaries will be provided for the Safety Analysis Set.

Dosing information for individual participants will be listed.

4.2.2. Study Drug Administration for VES

Study drug administration for VES for participants in the Safety Analysis Set will be summarized for the following items:

- Number and percentage of participants who received at least 3 VES doses, 4 VES doses, 5 VES doses, 6 VES doses, 7 VES doses, 8 VES doses, 9 VES doses, and 10 VES doses.
- Number and percentage of participants who received 6 mg VES on 1st dose
- Number and percentage of participants who received 6 mg VES on 2nd dose
- Number and percentage of participants who received 6 mg VES on 3rd dose
- Number and percentage of participants who received 8 mg VES on 3rd dose
- Number and percentage of participants who received 8 mg VES on 4th dose and onwards

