1.4. Rationale for Dose Selection

1.4.1. Rationale for Dose Selection of Vesatolimod

Dose selection for VES is supported by the available PK, safety, and PD data from the completed Study GS-US-382-1450 and Study GS-US-382-3961 in ART-suppressed PWH, as well as the completed Study GS-US-243-0101 in healthy volunteers (for further information, please refer to the VES IB). The results from these studies indicate that VES is generally well tolerated up to 12 mg administered as a single dose or multiple doses, given every 2 weeks. As a TLR7 agonist, VES is expected to activate its receptor on plasmacytoid dendritic cells or B cells and stimulate the production of cytokines. Therefore, AEs related to influenza-like symptoms may be expected. When administered alone in ART-suppressed PWH and in healthy volunteers, VES up to 8 mg is well tolerated, with mild and infrequent influenza-like AEs (eg, fatigue, headache), whereas individuals receiving VES at the 10 mg dose or higher more frequently experienced influenza-like AEs. The VES starting dose selected for this study is 6 mg, with the option for intraparticipant dose escalation to 8 mg at the third VES administration (Day 28), pending safety and tolerability of the 6 mg dose in each participant, with close safety monitoring. Participants who escalate to 8 mg VES may remain on 8 mg VES, or de-escalate to 6 mg VES, pending safety and tolerability of the 8 mg VES dose in that participant. Participants who de-escalate to 6 mg VES would remain on 6 mg VES for the remainder of the study. The proposed dose range of 6 mg to 8 mg VES is expected to provide exposures associated with activity, as evidenced by induction of ISGs and cellular activation observed at VES doses of 4 to 12 mg.

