8.6.2. Adverse Events

Clinical and laboratory AEs will be coded using the Medical Dictionary for Regulatory Activities (MedDRA). System organ class, high-level group term, high-level term, preferred term, and lower-level term will be attached to the clinical database.

Summaries (number and percentage of participants) of treatment-emergent AEs (by system organ class, high-level term [if applicable], and preferred term) will be provided. Additional summaries will include summaries for AEs by grade, investigator's assessment of relationship to study drug, and effect on study drug dosing.

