1.3. Sample Size and Power

The sample size in this study is determined based on practical considerations and empirical experience with similar types of studies. No sample size and power calculation were performed. Up to 25 participants will provide a preliminary assessment of descriptive safety, efficacy, and PK.

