3.4. Examination of Participant Subgroups

There are no prespecified participant subgroupings for efficacy and safety analyses.

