7.1.7. Summaries of Adverse Events and Deaths

TEAEs will be summarized based on the Safety Analysis Set.

A brief, high-level summary of the number and percentage of participants who experienced at least 1 TEAE in the categories described below will be provided. All deaths observed in the study will also be included in this summary.

The number and percentage of participants who experienced at least 1 TEAE will be provided and summarized by SOC, HLT, and PT as follows:

- TEAEs

For the AE categories described below, summaries will be provided by SOC and PT:

- TEAEs by severity
- TEAEs with Grade 3 or higher
- TEAEs with Grade 2 or higher

- TE treatment-related AEs
- TE VES-related AEs
- TE VRC07-523LS-related AEs
- TE CAP256V2LS-related AEs
- TE treatment-related AEs with Grade 3 or higher
- TE treatment-related AEs with Grade 2 or higher
- TE SAEs
- TE treatment-related SAEs
- TEAEs leading to death (i.e., Grade 5 AEs)
- TEAEs leading to premature discontinuation of any study drug
- TEAEs leading to premature discontinuation of study

Multiple events will be counted only once per participant in each summary. Adverse events will be summarized and listed first in alphabetic order of SOC (and HLT within each SOC if applicable), and then by PT in descending order of total frequency within each SOC. For summaries by severity grade, the worst severity will be used for those AEs that occurred more than once in an individual participant during the study.

In addition to the above summary tables, all TEAEs, Grade 3 or Higher TEAEs, TE SAEs, TE treatment-related AEs, Grade 3 or Higher TE treatment-related AEs, Grade 2 or Higher TE treatment-related AEs, and TE treatment-related SAEs will be summarized by PT only, in descending order of total frequency.

In addition, data listings will be provided for the following:

- All AEs, including whether the event is TE
- All SAEs
- All Deaths
- All AEs leading to premature discontinuation of any study drug

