7.7. Changes From Protocol-Specified Safety Analyses

There are no deviations from the protocol-specified safety analyses.

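### The SAP carries over only the discontinuation part of the protocol's AE summary by effect on dosing while declaring no deviation, and it does not tabulate the VES dose course after Dose 3

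*SAP*

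**What the plan says.** **Protocol.** VES starts at 6 mg, with an optional step to 8 mg. Section 1.4.1 places that step at the third dose; Section 5.3 allows either level at Doses 3 to 10. Section 1.4.1 adds: "Participants who escalate to 8 mg VES may remain on 8 mg VES, or de-escalate to 6 mg VES". Anyone reduced then stays at 6 mg. Section 7.7.2.2 has study drug withheld after a related Grade 3 event until it improves. For the analysis, Section 8.6.2 lists further AE summaries by grade, "investigator's assessment of relationship to study drug, and effect on study drug dosing".

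**SAP, adverse events.** The only dosing consequence summarised in Section 7.1.7 is "TEAEs leading to premature discontinuation of any study drug", apart from a line on leaving the study. Section 7.7 says: "There are no deviations from the protocol-specified safety analyses". Section 2.3, on changes from the protocol, mentions only the second interim analysis.

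**SAP, exposure.** Section 4.2.2 counts participants reaching each number of VES doses from 3 to 10, those given 6 mg at Doses 1, 2 and 3, and those given 8 mg at Dose 3. It ends with "Number and percentage of participants who received 8 mg VES on 4th dose and onwards". Section 4.2.1 lists each participant's dosing. Section 3.4 states: "There are no prespecified participant subgroupings for efficacy and safety analyses".

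**The concern.** Tolerability is part of the primary objective. In a single-arm study of up to 25 people, whether participants could stay on their VES dose is direct evidence on it. The protocol provides for two outcomes short of discontinuation: a dose withheld for toxicity, and a return from 8 mg to 6 mg. Neither has a summary. A participant reduced or held for an AE who then completes VES does not appear in the discontinuation table.

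The exposure table does not fill the gap. Its last line can be programmed in two ways that give different percentages from the same data, and neither counts reductions. Meanwhile SAP 7.7 tells the reader of the study report that the protocol's safety analyses were followed in full.

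**Working it through.** There is no sample-size or power figure to reproduce. SAP 1.3 says: "No sample size and power calculation were performed". The check is a comparison of passages plus an enumeration.

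**1. AE summaries by effect on dosing**

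| Possible effect | In the protocol | Summarised in SAP 7.1.7 |
|---|---|---|
| Discontinuation | 6.9.1, 7.7.2.3 | Yes, table and listing |
| Interruption or withholding | 7.7.2.2 | No |
| Dose reduction | 1.4.1 | No |

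Protocol 8.6.2 does not define effect on dosing. Section 7.6, writing of laboratory abnormalities, treats interruption, modification and discontinuation together, so a reading confined to discontinuation is hard to sustain.

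**2. What the 8 mg lines of SAP 4.2.2 can separate**

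Assume all ten doses are given, at most one escalation, and no return to 8 mg after a reduction. Treat the two 8 mg items (Dose 3; Dose 4 onward) as if cross-tabulated. The SAP plans only separate counts, so the real table shows less.

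*Escalation at Dose 3 only (Section 1.4.1).* The sequences are: never escalated (1), escalated and stayed (1), reduced at one of Doses 4 to 10 (7). Total 1 + 1 + 7 = 9.
- Last line read as *any* later dose: the sequence reduced at Dose 4 is separable. The other 7 − 1 = 6 look the same as staying on 8 mg.
- Read as *every* later dose: all 7 fall outside the group that stayed on 8 mg, but the timing is lost.

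*Escalation at any of Doses 3 to 10 (Section 5.3).* Sequences with a reduction: 7 + 6 + 5 + 4 + 3 + 2 + 1 + 0 = 28. Escalated without reduction: 8. Never escalated: 1. Total 37.
- *Any*: 6 sequences starting at Dose 3 plus 21 starting later, so 27 of 28, share a cell with a sequence that has no reduction.
- *Every*: 21 of 28 do.

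The participant dosing listing separates all of these sequences.

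**3. Size, by illustration**

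The documents give no escalation or reduction rate. Assume all 25 escalate at Dose 3, *r* are reduced at Dose 6, and nobody discontinues. Under *any* the line shows 25/25 for every *r*. Under *every* it shows (25 − *r*)/25.

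| *r* (assumed) | *Any* | *Every* |
|---|---|---|
| 0 | 100% | 100% |
| 5 | 100% | 20/25 = 80% |
| 10 | 100% | 15/25 = 60% |
| 15 | 100% | 10/25 = 40% |

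In each row the discontinuation table shows zero.

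**The case against.** **The data are not lost.** Dosing is listed by participant (SAP 4.2.1), and all AEs are listed (7.1.7) in chronological order (3). With at most 25 people the two can be linked by date. This stands. A reader might infer that the trial cannot report whether 8 mg was tolerated; the documents do not support that. What is missing is a planned summary.

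**The protocol summary is not dropped.** Its discontinuation part is kept as both table and listing, and 8.6.2 names no dose-reduction table. This also stands: the carry-over is partial. It does not rescue SAP 7.7, because withholding and reduction are effects on dosing in this protocol.

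**Pooling 6 mg and 8 mg is not a departure.** The primary objective concerns the regimen, Protocol 8.6 summarises safety by study drug received, and no by-dose AE table is requested. The SAP also separates VES-related TEAEs and VES-related potential CRS and flu-like events. A reader might infer that pooled AE tables breach the protocol; they do not. A by-dose table could even mislead. Protocol 1.5 says VES-related AEs are more common after Doses 1 and 2, which are always 6 mg. Most doses that could be 8 mg fall after ART stops, and those who escalate have tolerated 6 mg.

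**The dose step is not the only tolerability decision.** A reader might treat it so, but the protocol also has rules on discontinuation (6.9.1), infusions (5.3), CRS (7.7.1), and Grade 3 and 4 events (7.7.2.2, 7.7.2.3).

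**Small cells.** SAP 1.3 claims no more than this: "Up to 25 participants will provide a preliminary assessment of descriptive safety, efficacy, and PK". That limits what the tables can show but is no reason to omit counts. Protocol 1.2.4.1.2 itself reports AEs from an earlier VES study by dose sequence, in VES groups of 2 to 5.

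**Conclusion.** The point holds as a reporting defect with two parts. First, SAP 7.1.7 implements one of three kinds of effect on dosing, and SAP 7.7 is inaccurate in declaring no deviation. This rests on reading effect on dosing to include withholding and reduction, which Protocol 7.6, 7.7.2.2 and 1.4.1 support. Second, SAP 4.2.2 does not describe the VES dose course after Dose 3. Its last line is ambiguous, and, under the enumeration's assumptions, the *any* reading leaves 6 of 7 or 27 of 28 reduction sequences indistinguishable from one without a reduction.

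The percentages in the illustration are assumed; the actual effect depends on how many participants escalated and were reduced, which the documents do not state. The primary endpoints, the proportions with TEAEs and with graded laboratory abnormalities, are unaffected. Nothing here bears on which VES dose is appropriate.

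**What to change.** 1. **SAP 4.2.2.** Replace the last line with the number and percentage receiving 6 mg and 8 mg at each of Doses 3 to 10, the number ever escalated, and the number de-escalated. Give the reason for de-escalation if the eCRF captures it.
2. **SAP 7.1.7.** Add TEAEs leading to interruption, withholding or dose reduction of VES.
3. **SAP 7.7.** If item 2 is not done, declare the omission and give the reason.
4. **Optional.** A table of TEAEs by last VES dose before onset may be shown. It must be labelled descriptive and confounded by dose order, ATI and selection of participants who tolerated 6 mg.

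The cost is a few descriptive tables with small cells. The dose counts come from the study drug administration eCRF named in SAP 3.8.1. The AE table needs the action taken on study drug; Protocol 8.6.2 presupposes that this was recorded, but the eCRF is not available to confirm it. The SAP is final and an ad hoc analysis has already been run (SAP 2.3), so the tables should be recorded as late additions. SAP 1 provides for documenting such changes in the clinical study report.

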4.2.3. Study Drug Administration for VRC07-523LS and CAP256V2LS

Study drug administration for participants in the Safety Analysis Set will be summarized for the following items:

- Number and percentage of participants who received IV infusion of VRC07-523LS on Day 7.
- Number and percentage of participants who received IV infusion of CAP256V2LS on Day 7.

4.3. Protocol Deviations

Participants who did not meet the eligibility criteria for study entry but enrolled in the study, will be summarized regardless of whether they were exempted by the sponsor or not. The summary will present the number and percentage of participants who did not meet at least 1 eligibility criterion and the number of participants who did not meet specific criteria based on the All Enrolled Analysis Set. A by-participant listing will be provided for those participants who did not meet at least 1 eligibility (inclusion or exclusion) criterion. The listing will present the eligibility criterion (or criteria if more than 1 deviation) that participants did not meet and related comments, if collected.

Protocol deviations occurring after participants entered the study are documented during routine monitoring. The number and percentage of participants with at least 1 important protocol deviation will be summarized for the All Enrolled Analysis Set. Additionally, the number and percentage of participants with at least 1, 1, 2, or 3 or more important protocol deviations will be summarized. The total number of important protocol deviations will be summarized by deviation category. A by-participant listing will be provided for those participants with protocol deviations, included a column specifying whether the protocol deviation is important.

4.4. Assessment of Disaster or Public Health Emergency Impact

This study was ongoing during the novel coronavirus (COVID-19) pandemic which had an impact on the study conduct. Some participants may have been unable to attend onsite visits due to shelter in place guidelines, site closures, or other reasons. This section describes how special situations due to COVID-19 will be handled in the analysis. Please refer to [Appendix 2](#) for data collection and determination of COVID-19 impact Data.

4.4.1. Study Drug or Study Discontinuation Due to Disaster or Public Health Emergency

A by-participant listing of reasons for premature study drug or study discontinuation due to COVID-19 will be provided if applicable.

4.4.2. Protocol Deviations Due to Disaster or Public Health Emergency

A by-participant listing will be provided for participants with protocol deviations related to COVID-19 if applicable.

